### Section I. Purpose, Background and Rationale

### A. Specific Aims and Hypotheses

In the proposed randomized controlled trial, we seek to determine the feasibility and efficacy of a combined breastfeeding, DPP-based program in a cohort of overweight/obese women to be followed during pregnancy through 6 months postpartum. Our trial will have three study arms: DPP plus breastfeeding (Tx1); DPP Only (Tx2); and Usual Care (Tx3). Specific aims are:

Aim 1: Test the efficacy of Tx1 to improve 6-month postpartum weight loss among women with a BMI  $\geq$  25. We will measure maternal height and weight at baseline; weight at delivery and 6 months postpartum.

Hypothesis 1: Women in Tx1 will have greater weight loss postpartum compared to women in Tx2 and Tx3.

Aim 2: Test the efficacy of Tx1 to improve 6-month postpartum mean blood glucose (HbA1c) and mean arterial blood pressure among women with a BMI  $\geq$  25. We will measure HbA1c and mean arterial blood pressure at baseline, delivery, and 6 months postpartum. Hypothesis 2: Women in Tx1 will have better HbA1c and mean arterial blood pressure postpartum compared to women in Tx2 and Tx3.

Aim 3: Test the efficacy of Tx1 to increase any breastfeeding through 6 months postpartum among women with a BMI  $\geq$  25. We will measure any breastfeeding continuance at week 1, 3, and 6 postpartum, and at 3 and 6 months.

Hypothesis 3: Women in Tx1 will breastfeed longer compared to women in Tx2 and Tx3.

# B. Background and Significance

Gestational diabetes mellitus (GDM) affects between 6% to 20% of pregnant women in the United States. Overweight and obesity are a major risk factor for GDM and also considered an independent risk factor for other adverse health outcomes. Women with a history of GDM have at least a seven-fold increased risk of developing type 2 diabetes mellitus (T2DM) compared to women who do not have GDM. Gestational diabetes is associated with increased maternal and neonatal morbidity and mortality. Complications of GDM are further increased for rural women who often experience limited access to obstetrical healthcare services, leading to poor birth outcomes and reduced breastfeeding rates.

Against this background, we completed a pilot health assessment in a rural southwest Kansas community with an alarming number of high-risk pregnancies complicated by gestational diabetes, 11% vs. 6% nationally. Half of respondents were Hispanic of low socio-economic status. During pregnancy, three-quarters of women were overweight/obese, did not exercise, and had a family history of diabetes. Further, findings from a qualitative follow-up study within this same community indicated that women had limited access to health promotion programs and breastfeeding services.

Rural communities with limited availability of health promotion programs and potentially high rates of chronic disease face a myriad of problems. First, diabetes is associated with adverse health outcomes for mother and child. Women with GDM are at increased risk for pregnancy and delivery complications — including preeclampsia, 18-22 cesarean section, 18,19,22,23 pregnancyinduced hypertension,  preterm birth,  shoulder dystocia,  and macrosomia -27,29 — leading to increased maternal and neonatal morbidity and mortality. 18,24,29,39 Infants born to mothers with GDM are more likely to have neonatal hypoglycemia,  hyperinsulinemia,  and are at greater risk for developing metabolic syndrome, 41 diabetes, 42 and obesity during childhood/adolescence. 43-45 Second, having a pregnancy complicated with GDM and residing in a rural location is particularly challenging due to limited access and availability of healthcare services. 46-51 Specifically, rural pregnant women have a higher likelihood of low birth-weight babies and pre-term delivery,  high smoking rates,  and reduced breastfeeding rates.  Due to geographic barriers, high rates of chronic disease including obesity, and limited availability of health promotion programs coupled with a demonstrated need for health behavior change, it becomes important to test an intervention during the prenatal and postnatal period among this at-risk population. This period is particularly conducive to behavior change because: (1) women are more likely to modify their behavior to benefit their children, (2) behavior change interventions are most successful in the short term, and (3) effective interventions that start during pregnancy are more likely to be sustained after birth, thereby reducing the risk of retaining excess weight and maternal obesity. 53,54

Given the demonstrated need for health behavior change, it is worthwhile to test the use of an intervention during the prenatal and postnatal period. The Diabetes Prevention Program (DPP) is associated with a reduced risk of developing T2DM by 58% through counseling on effective

diet, exercise, and behavior modification. There is also evidence to support the use of this efficacious program in reducing postpartum weight. Further, recent evidence suggests that longer duration of breastfeeding is associated with lowering T2DM incidence, reducing maternal postpartum weight, and resetting maternal metabolism after pregnancy. Breastfeeding also protects against breast cancer, ovarian cancer, and T2DM. Despite these findings, no studies have addressed the role of intensive breastfeeding support combined with an efficacious weight loss program to reduce postpartum weight, thereby reducing progression to T2DM after pregnancy.

The American Academy of Pediatrics and the World Health Organization recommend breastfeeding for the first 6 months of life. In Kansas,  $79\%^{73}$  of women with a BMI  $\geq 25$  start breastfeeding, and only  $29\%^{73}$  still breastfeed with some supplementation (defined as "any breastfeeding") at 6 months postpartum. The Kansas rate for high BMI women of 29% is unacceptable and an urgent public health concern when compared to the 6-month breastfeeding rate for normal BMI Kansas women of 51% and the Healthy People 2020 goal of 61%. In the proposed randomized controlled trial, we seek to determine the feasibility and efficacy of a combined breastfeeding, DPP-based program in a cohort of overweight/obese women to be followed during pregnancy through 6 months postpartum. Our trial will have three study arms: DPP plus breastfeeding (Tx1); DPP Only (Tx2); and Usual Care (Tx3). A total sample of 60 pregnant women in their 1st or 2nd trimester with a BMI  $\geq 25$  will be recruited. Eligible participants are randomly assigned to a study arm (20 per arm).

### C. Preliminary Studies

I led and completed two pilot studies in southwest rural Kansas: (1) a health assessment of the obstetrical population (completed in April 2015), and (2) a follow-up focus group study with the same population (completed in May 2016). The purpose of the assessment was to learn about the health behaviors of rural pregnant women. Two local hospitals and one federally qualified rural health center participated in the assessment. Our sample consisted of 177 rural pregnant women. Key findings indicated that the majority of women were Hispanic (50.3%), 18-25 years old (48.6%), high school educated (51.2%), WIC enrolled (51.7%), and earned < \$25,000/year (54.2%). The majority were overweight (28.1%) or obese (26.2%) *prior* to pregnancy, which increased to 34.4% and 41.6% respectively during pregnancy. Additionally, the majority engaged in no daily exercise (72.6%) and nearly one-third (30.5%) reported having an immediate family member who was diagnosed or treated for diabetes or cardiovascular disease. These results demonstrate significant diabetes risk factors during and after pregnancy. Subsequently, in follow-up to the assessment, I led and completed a focus group study to gain in-depth information from this same population on what they would value in a health promotion program. Findings indicated limited availability of programs that focus on exercise, diet, and breastfeeding support during and after pregnancy. Further, I published three additional studies relevant to the proposed project. Each of these studies focused on health behaviors among urban versus rural WIC enrolled women in Kansas and helped our research team understand the prenatal and postnatal needs of at-risk populations in Kansas. These studies also provided me with

experience in collaborating with other researchers and with the process of publishing a manuscript in a high-impact professional journal.

### D. Rationale for Proposed Study

Risk factors for diabetes are well documented. Maternal obesity in particular increases the risk of negative health outcomes for mother and child,  including the propensity for women to retain excessive postpartum weight leading to obesity in subsequent pregnancies. 87-90 Less is known about protective factors relevant to diabetes though evidence suggests that longer duration of breastfeeding among women with a history of GDM is associated with lower incidence of developing type 2 diabetes up to two years after pregnancy. 58-61 Breastfeeding also appears to lower maternal postpartum weight and facilitates the resetting of maternal metabolism after pregnancy. 65 The Diabetes Prevention Program (DPP) is associated with a reduced risk of developing diabetes by 58% and there is evidence to support the use of this efficacious program in reducing postpartum weight.  Despite these findings, no studies have used a DPP-enhanced version that includes intensive breastfeeding counseling and support for overweight and obese women. Given that overweight and obese women at risk for GDM are also less likely to start and continue breastfeeding, 84,91-93 it is critical that interventions for reducing GDM risk also include breastfeeding support that is uniquely tailored to the needs of this population. This is where the current proposal narrows the gap and contributes to the body of knowledge about reducing diabetes risk factors during and after pregnancy in an underserved population with scarce healthcare resources available.

# E. Impact of Proposed Study

The proposed project will inform future intervention efforts that aim to reduce diabetes risk factors during and after pregnancy and to increase breastfeeding, thereby improving short- and long-term maternal and child health outcomes. The immediate impact will be to reduce diabetes risk factors among a high-risk population and inform interventions aimed at reducing these risk factors and decreasing disproportionate morbidity. Its ultimate potentially high public health impact is GDM and type 2 diabetes prevention among a racially and ethnically diverse, at-risk population.

### F. Justification for Project

Risk factors for diabetes are well documented, but less is known about some factors that attenuate the risk for GDM. Recent studies support the use of the Diabetes Prevention Program in reducing postpartum weight. Moreover, emerging research suggests that longer duration of breastfeeding among women with a history of GDM decreases the likelihood of developing type 2 diabetes within two years after pregnancy. However, no prior studies have assessed the feasibility and efficacy of a DPP-based intervention that includes intensive breastfeeding counseling and support among racially and ethnically diverse reproductive-age rural women. Rural pregnant women in particular have decreased access to healthy foods and fewer options to engage in physical activity. Furthermore, Hispanic women often supplement breastfeeding with formula, triggering decreased milk supply and early breastfeeding cessation. The

proposed research is *innovative* because it represents a departure from what has been accomplished in the field thus far: *We seek to implement a combined breastfeeding, DPP-based intervention and determine its feasibility and efficacy as well as its effect on metabolic outcomes among an at-risk population. Through examination of postpartum weight, breastfeeding behavior, and metabolic markers, results of the proposed project will inform the development of interventions to reduce diabetes risk factors during and after pregnancy. Furthermore, an efficacious approach toward promoting exercise, nutrition, and breastfeeding can be integrated into the continuum of healthcare services provided to racially and ethnically diverse, at-risk rural pregnant women.* 

## Section II. Research Plan and Design

#### A. Study Design Overview Figure 1. Study Design Screen individuals for eligibility After meeting study inclusion criteria, randomize individuals into Tx1, Tx2, or Tx3 Tx2 Tx3 Intervention (Tx1) **DPP** plus **DPP Only Usual Care** Breastfeeding (N=20) (N=20) (N=20) Ρ DPP - 16 sessions: Core Regular prenatal care DPP - 16 sessions: R R provided by physician curriculum (Phase I) Core curriculum (Phase I) E Е **Breastfeeding Education** N Ν 2-hour curriculum Α Α (between weeks 20 - 24) т т Breastfeeding Booster Α Α Session 1-hour curriculum L L (between weeks 28 - 32) Р At delivery – in-hospital At delivery - in-hospital At delivery - in-hospital 0 breastfeeding support breastfeeding support breastfeeding support s DPP - 15 sessions: Post-DPP - 15 sessions: Т core curriculum (Phase II) Post-core curriculum N (Phase II) Α **Breastfeeding** т Т Assessment (at five Α Α separate time points)

This is a three-arm pilot randomized controlled trial (RCT) to implement as well as determine the feasibility and efficacy of an intervention that is based on the Diabetes Prevention Program and includes intensive breastfeeding counseling and support among a cohort of overweight and obese pregnant women. Upon meeting eligibility criteria, participants will be randomly assigned to the DPP plus breastfeeding (intervention, Tx1), DPP Only (Tx2), or Usual Care (Tx3), and will be followed during pregnancy through 6 months postpartum. Participants in Tx1 will receive the DPP and targeted breastfeeding support during pregnancy through 6 months postpartum. Participants in Tx2 will receive the DPP only. Participants in

Tx3 will receive care as usual. Usual care is described as obstetrical care that women with normal BMI receive and that is provided by the same provider ([name]).

At recruitment and at study closure, participants will complete four survey instruments; each of which assesses women's knowledge of physical activity, nutrition, and breastfeeding (see appendices 1 through 4). Also, postpartum women will complete the Edinburgh Postnatal Depression Scale (EPDS, see appendix 5) and a study coordinator will assess postpartum women's breastfeeding experience with the Bristol Breastfeeding Assessment Tool (BBAT, see

appendix 6). Weight, mean blood glucose (HbA1c), mean arterial blood pressure, and glucose tolerance levels during pregnancy as well as initiation and duration of breastfeeding will be measured for all participants through 6 months postpartum.

### **B.** Duration of Study

It is anticipated that after receiving Institutional Review Board (IRB) approval, recruitment will begin during the last quarter of 2019 and will continue through June of 2020. We will recruit over a period of 9 months and the last follow up with women will take place at 6 months postpartum. The trial will be completed over a 24-month period and will conclude during the second quarter of 2021. Data collection and preliminary data analysis will take place as the trial runs. Final data analysis and dissemination of findings will all take place following completion of the trial, during 2021 and 2022.

### C. Number of Participants

This IRB protocol pertains to the recruitment of eligible participants from two obstetrical clinics: one clinic at Via Christi Health (VCH), a regional hospital in Wichita, and another clinic at Kearny County Hospital, a full-service hospital in rural southwest Kansas. About 45% (16,797) of Wichita's Hispanic population is female and of reproductive age, 102 and the VCH clinic sees a high volume of this at-risk population at an average of 123 pregnant patients per month, with an average pre-pregnancy BMI of 30.5 (personal communication by senior management staff at VCH on January 18, 2017). These socio-demographic and health data are similar to those of atrisk rural pregnant women in southwest Kansas who visit Kearny County Hospital (KCH) for prenatal and postnatal care. [name], maternal fetal medicine specialist, sees pregnant women at both of these locations (VCH and KCH), and he and his staff will actively assist with patient recruitment. Our goal is to randomize a total of 72 eligible participants (24 women in each study arm, which translates to 12 women from each recruitment site). Our recruitment target of overweight or obese pregnant women will involve 50% Hispanic women (who are English-speaking) and 50% other race including non-Hispanic whites. The population of pregnant women in southwest Kansas who deliver at Kearny County Hospital, Lakin, Kansas, is estimated to be 300 individuals, of which 75% (or 225 individuals) have a BMI  $\geq$  25 and  $\leq$  35.

### D. Subject Selection Criteria and Recruitment

We will recruit pregnant patients from two obstetrical clinics: one clinic at Via Christi Hospitals Wichita, Inc. (VCH), a regional hospital in Wichita, and another clinic at Kearny County Hospital, a full-service rural hospital located in Lakin, southwest Kansas. [name], maternal fetal medicine specialist, sees pregnant women at this location, and he and his staff will actively assist with patient recruitment. During the first prenatal appointment, [name] will screen potential participants for inclusion criteria, and if he believes a participant meets inclusion criteria (see Table 1), then he will familiarize a potential participant with the study's purpose. If the potential participant is interested in the study, then he will give her a study brochure and a hard copy of the consent form. Prior to using this study brochure, the brochure will be reviewed and approved by the IRB at Via Christi Hospitals Wichita, Inc. By providing the potential

participant with a copy of the consent form, this will serve as the verbal consent script. [name] will also provide the potential participant's name and phone number to [name] and her research coordinator. After receiving a potential participant's name and phone number from [name], the research coordinator will follow up with a phone call to determine if the potential participant again meets study inclusion criteria, and if she does, the coordinator will screen if the potential participant meets study exclusion criteria during the same phone call (see Table 1). Before the research coordinator screens for inclusion and exclusion criteria, during this same phone call, verbal consent will be obtained between the participant and the research coordinator, using the consent form as the verbal consent script, and then written e-consent will be obtained via REDCap at the orientation session. Once the participant is enrolled in the study and over the course of her pregnancy develops one of the conditions mentioned under Exclusion (Table 1), then this will be reported to the Data and Safety Officer. It will then be decided in consultation with [name] if the participant will be able to continue participating in the study or if she will need to be dismissed.

Table 1. Enrollment Criteria

Inclusion
1. Pregnant
2. In 1st trimester or early in 2nd trimester
2. BMI ≥ 25 and < 35
3. At least 18 years old or older
Be able to understand English
5. Must have a cell phone
6. Able to use Facebook
7. Able to use Skype, FaceTime or Zoom
Exclusion
Pregnancy complications that require emergency care
2. Thyroid disease
3. Multiple gestation
4. Substance abuse within last 3 years
5. ART (Assisted Reproductive Technology) pregnancy
6. Current smoker
7. Prior bariatric surgery
8. In weight-loss program within 3 months of conception
9. BMI ≥ 35
10. Unable to attend intervention/follow-up visits
11. Unwilling to self-monitor data collection
12. Unable to complete intervention
13. Presence of any condition that limits walking
14. Presence of any condition that limits following diet
recommendations
15. Pregnancies complicated with fetuses diagnosed with
lethal malformations/conditions

If the participant meets enrollment criteria, then the research coordinator will call her again to assign her a time and place for the orientation session, to complete study-related survey instruments, and to obtain her email address to provide her with informed consent materials for review. Participants are informed that they will earn incentives to continue and complete the study: (1) a \$50 gift card at study entry, (2) a digital scale and pedometer at delivery, and (3) a gift up to \$75 for baby at Walmart's baby registry at study closure. Investigators will issue incentives in accordance with policies set forth by

IRB (please refer to the heading titled "Self-Administered Surveys and Incentive to Participate" below for additional detail regarding participant incentives).

Our recruitment target of overweight or obese pregnant women will involve 50% Hispanic women (who are English-speaking) and 50% other race including non-Hispanic whites. We anticipate meeting our recruitment goals through multiple approaches. We will promote the study via targeted mailings and clinic posters. We will advertise and develop study materials in English only. We will recruit over a period of 9 months, planning to randomize 2-3 participants

each week, or 1-2 participants per site. Our goal is to randomize a total of 72 pregnant women (24 women in each study arm, 12 women per site). Given an attrition rate of 20%, this will leave us with 60 women total (20 women in each study arm, or 10 women per site in each study arm).

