Sample Size and Randomization. The primary outcomes of interest are: (1) postpartum weight loss; (2) HbA1c and mean arterial blood pressure; and (3) breastfeeding duration. A total of 60 participants (20 per study arm) will be recruited. The results from this pilot study will be used in sample size estimation for a future study that is sufficiently powered to detect a clinically meaningful effect size. Due to the nature of this project being a feasibility study, the sample size in the proposed study is not based on providing adequate power to detect a clinically meaningful effect size across the three study arms. Block randomization with block size of 5 participants will be employed. A sequence of 12 random integers will be generated using a computer algorithm. The first 4 integers of the sequence will be assigned to the DPP plus breastfeeding arm; the next 4 integers will be assigned to the DPP only arm; and the last 4 will be assigned to the usual care arm. Blocks will be assigned to arms in the increasing order of sequence of integers generated.

**Statistical Analysis.** For baseline data characteristics, descriptive statistics will be reported as mean and standard deviation for continuous variables and as count and percentage for categorical variables. Depending on the distribution of the continuous variables, the Kruskal-Wallis test or ANOVA will be used to test for differences in continuous variables across the three arms. Chi-

Square test of independence (or Fishers exact test if 25% of cells have counts less than 5) will be used to assess the association between categorical variables and the three arms. The analysis will be based on "intention-to-treat" principle. A two-sided alpha level of 0.05 will be used to determine statistical significance. A 95% confidence interval will also be reported.

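### Women who develop an exclusion during pregnancy may be dismissed from the study, and the plan neither keeps them in follow-up nor reconciles this with its intention-to-treat analysis

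*Combined protocol and SAP*

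**What the plan says.** Section II.A places randomisation directly after eligibility: "Upon meeting eligibility criteria, participants will be randomly assigned to the DPP plus breastfeeding", or to one of the other two arms. An exclusion that appears later in pregnancy is therefore a post-randomisation event.

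Section II.D covers that case. If an enrolled woman "develops one of the conditions mentioned under Exclusion (Table 1), then this will be reported to the Data and Safety Officer", it is then decided, after a further consultation, "if the participant will be able to continue participating in the study or if she will need to be dismissed". The rule concerns leaving the study, not only the sessions. It gives no criteria, does not say whether the decision-makers know the arm, and does not say what happens to follow-up.

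The rule refers to the whole Table 1 exclusion list. Besides medical conditions, the list contains a BMI of 35 or more (item 9) and three participation items: "10. Unable to attend intervention/follow-up visits", "11. Unwilling to self-monitor data collection" and "12. Unable to complete intervention".

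Section III, Statistical Analysis, states: "The analysis will be based on 'intention-to-treat' principle". It defines no analysis set. The Missing data paragraph treats attrition and nonresponse as missing at random. It uses complete cases when less than 5% is missing and multiple imputation otherwise, with last observation carried forward for postpartum weight. Under Aim 3, women lost to follow-up are censored in the Cox model. Section IV.B.a stops further collection and use of data only when consent is withdrawn. Dismissal is not mentioned there.

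**The concern.** An intention-to-treat comparison needs outcomes on the women who were randomised, grouped as randomised. A rule that lets the study team remove a woman afterwards is harmless only if she is still followed, or if removal is unrelated to arm and prognosis. The plan secures neither.

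Some triggers are plainly linked to arm. The two DPP arms have 16 prenatal and 15 postnatal sessions to complete; usual care has none. Section IV.A.b describes activity and nutrition monitoring as a requirement of the DPP. Section II.F & G has the coordinator phone participants weekly about module progress, so a difficulty with participation is more likely to come to light in a DPP arm. Item 9 is different: it lies on the pathway to weight, a primary outcome, and a lifestyle programme in pregnancy is meant to act on weight.

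What is at stake is whether the arms compared at 6 months are still the randomised arms. The retention figures and effect estimates that this pilot is meant to supply for a larger trial are exposed in the same way.

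**Working it through.** **1. The plan's own numbers.** Sections II.C and II.D give 72 randomised, 24 per arm, falling to 60 (20 per arm) after 20% attrition. Recomputed: 72 × 0.80 = 57.6 in total and 24 × 0.80 = 19.2 per arm. Going from 24 to 20 is a loss of 4/24 = 16.7%. This small mismatch is a separate matter and nothing below depends on it. The plan does not say whether dismissals count within the attrition allowance.

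**2. Weight of one dismissal.** 1/24 = 4.2% of a randomised arm.

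**3. Which exclusions can arise after randomisation.**
- Cannot newly arise: assisted-reproduction pregnancy, prior bariatric surgery, a weight-loss programme within 3 months of conception.
- Can arise and can be affected by arm: items 10, 11 and 12.
- Can arise and lies on the weight pathway: item 9.

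**4. Can a participant reach BMI 35 in pregnancy?** Gain needed = (35 − BMI) × height². Height is an assumption, because the documents give none.

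| BMI at start | 1.60 m (h² = 2.56) | 1.63 m (h² = 2.66) |
|---|---|---|
| 30.5 (clinic mean before pregnancy, Section II.C) | 4.5 × 2.56 = 11.5 kg | 12.0 kg |
| 32 | 3 × 2.56 = 7.7 kg | 8.0 kg |
| 33 | 2 × 2.56 = 5.1 kg | 5.3 kg |

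The survey in Section I.C puts overweight and obesity before pregnancy at 28.1% and 26.2%, "which increased to 34.4% and 41.6% respectively during pregnancy". Obesity therefore rose by 41.6 − 26.2 = 15.4 points. This shows that BMI categories shift in pregnancy; it does not count women crossing 35.

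**5. A woman dismissed before delivery and not followed, taken through each analysis.**
- *Aim 1.* The first of the six weights is at delivery. She has none of the six, so none of the five consecutive differences exists and there is no postpartum value to carry forward.
- *Aim 2.* She has no 6-month HbA1c or blood pressure. If fewer than 5% are missing, she is dropped: 0.05 × 72 = 3.6, so up to 3 women (3/72 = 4.2%) fall under the complete-case rule, while 4 women (5.6%) do not. Above that threshold, imputation assumes missing at random, although a discretionary removal for adherence or weight gives no reason to expect this.
- *Aim 3.* She has no breastfeeding time at risk, so censoring her in the Cox model adds no information. Her binary outcome is missing from the modified Poisson model.

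**6. Size of any bias.** Let f be the share of an arm dismissed and g the mean outcome of kept women minus that of dismissed women. The arm's mean among kept women differs from its full randomised mean by f × g. One dismissal (f = 1/24) moves it by 4.2% of g. The bias in an arm comparison is f₁g₁ − f₂g₂. The documents give no f or g for any arm, so neither size nor sign can be filled in.

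**The case against.** The best defence is that the text does less than it may appear to. Review is case by case and dismissal is only one possible result. No section says a dismissed woman's data are discarded; only withdrawal of consent has that effect. The plan also compares imputed with complete-case results. This stands as far as it goes: a reader might infer that the rule undoes the intention-to-treat analysis, and the documents do not show that. They leave her status undefined.

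A second defence is that the rule is a safety provision about conditions that develop, addressed to a safety officer. Slow progress is handled elsewhere, by extra time and video help, and completion of the DPP is counted as a feasibility outcome. Table 5 schedules no maternal weight between baseline and delivery, so the study itself has no prenatal measurement to trigger item 9. These points make frequent dismissal under items 9 and 12 less likely. They do not remove those items from the rule, which refers to the exclusion list without limit. It also follows that these items can be affected by arm, not that they are consequences of randomised treatment; the documents do not establish causation.

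Third, a reader might infer that usual care would lose its heaviest gainers and so look better than it is. The documents do not support a direction. Aim 1 measures loss from delivery onward, and nothing says a woman with a high delivery weight then loses less; if she loses more, removing her makes usual care look worse. Dismissal of non-completers would act on the DPP arms instead.

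Finally, this is a pilot not powered for efficacy, and it already records withdrawals with reasons. That limits the consequence. But the plan still tests at a two-sided 0.05 and will use the results to size a further trial, and neither dismissals nor reporting by arm is mentioned among the recorded items.

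**Conclusion.** The concern holds as a risk to the intention-to-treat analysis that the plan leaves open. A discretionary post-randomisation rule allows dismissal from the study. Four of its triggers (items 9 to 12) can be affected by arm or lie on the weight pathway. Nothing keeps dismissed women in follow-up, and the missing-data rules do not protect against removal related to arm. Each dismissal is 1 of 24 randomised per arm (4.2%).

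This conclusion rests on reading the rule as covering every Table 1 item that can arise in pregnancy, and on dismissed women not being followed, since no section provides for it. How many dismissals would occur, and the direction and size of any bias, cannot be determined from the documents. The gains needed to reach BMI 35 depend on assumed heights and show only that the threshold can be crossed. The plan should be changed here, because the protection is simple and the gap touches all three aims.

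**What to change.** Reconcile Section II.D with the intention-to-treat statement in Section III by separating two events: stopping the sessions and leaving the study.

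- In Section II.D, state that whatever is decided about the sessions, a woman who has not withdrawn consent stays in follow-up for the Table 5 maternal outcomes, and for the infant and feeding outcomes where they apply. The qualification matters because Table 1 includes lethal fetal conditions.
- In Section III, state that every randomised woman is analysed in her assigned arm, including any who stopped the sessions under this rule.
- Add dismissals, by arm and reason, to the pilot's recorded withdrawal data.

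The cost is a few sentences and a small amount of extra follow-up at time points already scheduled in Table 5. The clinical decision about whether a woman continues the sessions is not addressed here.
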